#### 4.3 Follow- up procedures (by visits)

The TEMPO program has additional components that extend beyond the hospital period. Parent and infant outcome measures will be collected at the first follow-up and 12 month corrected age follow-up clinic visits. Please see Table 1: Study Events and Figure 1: Study Scheme in the Appendix for a complete timeline.

After hospitalization:

- **Visit 1: Parent Education Post-Discharge:** The PT will call the parent within 2 weeks of discharge to follow up about discharge education and massage. During this phone call, the PT will review the home program and massage techniques. The PT will also answer any parent questions. Therapist email and pager information will be provided.
- **Visits 2-12 (approximate): Bi-weekly emails:** The PT will send bi-weekly emails with developmental play activity and massage reminders and tips from hospital discharge through the first follow up appointment.
  - These emails will include a link for parents to report frequency of PT intervention and massage at home.
- **Visit 13 (approximate): First Visit Follow-up Massage Review Session:** At the infant's first follow-up appointment with the multidisciplinary neonatology team, the PT will provide a gross motor screening assessment and education. In addition, as part of the TEMPO program, a PT will facilitate a parent-administered infant massage session to provide an opportunity for parent to receive feedback on technique from the PT. This session will address any safety concerns, infant changes, and parent questions.
  - At this visit, the therapist will have the parent fill out the following questionnaires for ongoing measurement: AIM, FIM, PROMIS, CESD, EPDS, PSOC
  - At this visit, the PI or study coordinator will interview the parent about acceptability of the TEMPO program.
- **Visits 14+ (approximate): Bi-weekly emails:** The PT will continue to send bi-weekly emails with developmental play activity and massage reminders until the 12 month follow up appointment.
  - These emails will include a link for parents to report frequency of PT intervention and massage at home.
- **12 Month Follow-up Appointment:** At the standard of care 12 month corrected age follow-up appointment with the multidisciplinary neonatology team, the PT will administer a standardized assessment of gross and fine motor skills (Bayley Scales of Infant Development-III).
  - At this visit, the therapist will have the parent fill out the following questionnaires for ongoing measurement: AIM, FIM, PROMIS, CESD, EPDS, PSOC (Aim 1)

- Additionally, the parent will complete the PAQ questionnaire. (Aim 1)
- At this visit, the PI or study coordinator will interview the parent about acceptability of the TEMPO program. (Aim 1, Aim 2)

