Subject Population key criteria for Inclusion and Exclusion:	
Inclusion Criteria: Infants with gestational age <math><28</math> weeks gestation, within the first 3 weeks of life, and their biologic mother or father. Parent must be able to speak and understand English.
 
Exclusion Criteria: Infants who do not have a biological parent available to consent within the first 3 weeks of life. Infants with genetic/chromosomal abnormality, congenital neurological or musculoskeletal disorder, or abnormal bone density that would affect the ability to do massage and/or exercise and the safety of the infant. Parents who are unwilling to engage in all components of TEMPO.

Number Of Subjects	30 infant-parent dyads
Study Duration	
Each parent-infant dyad's participation will last approximately 15 months.
 
The entire study is expected to last approximately 27-28 months.

Study Phases	
 
• Screening: Once a PT referral is received for an infant born at <28 weeks gestation, the PI will be notified by the receiving therapist and an IRB-approved study team member will approach the biologic mother and/or father of the infant to discuss the study.
 

Screening	
Study Treatment	
Follow-Up	
 
• Intervention: The components of TEMPO are evidence-based and include infant massage, PTIs including developmental support and play activities to promote infant behavioral-motor development, principles of family-centered care, and multiple modes of educational delivery to enhance parent retention of knowledge and confidence in continuing PTIs after discharge.
 
• Follow-Up: Follow-Up after hospital discharge will include clinic visits at 2 and 12 months corrected age.
 

Safety Evaluations	
The physical therapist, with the assistance of the bedside nurse, will monitor vital signs continuously (heart rate, oxygen saturation, and respiratory rate) during all massage and physical therapy interventions. If the infant demonstrates any of negative responses during massage or PTIs, then the PT will adjust the treatment session accordingly to focus on developmental support that the infant can tolerate, while continuing to educate the parent about their infant's cues and behavior.

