## **5 STUDY EVALUATIONS AND MEASUREMENTS**

Variables that will be abstracted from medical charts:

 
○ Infant:
 
○ Name
 
○ Date of birth
 
○ Gestational age at birth
 
○ Birth weight
 
○ Race/ethnicity
 
○ Salivary Cortisol (post-salivary swab test)
 
	
 
○ Parent:
 
○ Name
 
○ Age
 
○ Race/ethnicity
 
○ Highest education completed (if available)
 
○ Salivary Cortisol (post salivary swab test)
 

--	--

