- Parent Interview: The parent who performed the study intervention will be interviewed at the first follow-up visit and the 12-month follow-up visit to obtain their insights on the feasibility, acceptability and perceived benefit of TEMPO. The PI or study coordinator elicit their feedback on program materials, intervention components, and factors that influenced whether they were able to continue the protocol at various time points post-discharge. For example: what they liked or disliked about the program, how often they did massage and for how long, did they find the massage easy to do on an ongoing basis, do they have suggestions to improve feasibility? We will also ask about willingness to have participated in this study if it were a randomized trial. This information will be critical to develop the planned trial (Aim 1 and 2). For example, should a parent not be willing to be randomized, the trial may need to randomize at some level other than individual infants/parents (e.g., hospital or a waitlist control condition).

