### Definitions

#### Adverse Event (AE)

An adverse event (AE) is any untoward medical occurrence in a subject during participation in the clinical study or with use of the experimental agent being studied. An adverse finding can include a sign, symptom, abnormal assessment (laboratory test value, vital signs, electrocardiogram finding, etc.), or any combination of these regardless of relationship to participation in the study.

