#### Serious Adverse Event (SAE)

A serious adverse event (SAE) is one that meets one or more of the following criteria:

- Results in death
- Is life-threatening (places the subject at immediate risk of death from the event as it occurred)
- Results in inpatient hospitalization or prolongation of existing hospitalization
- Results in a persistent or significant disability or incapacity
- Results in a congenital anomaly or birth defect

An important medical event that may not result in death, be life threatening, or require hospitalization may be considered an SAE when, based upon appropriate medical judgment, the event may jeopardize the subject and may require medical or surgical intervention to prevent one of the outcomes listed in this definition.

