#### Time Period and Frequency for Event Assessment and Follow-Up

An independent monitor has been identified to review enrollment, UPs, and AEs. The study team will send the independent monitor a report on enrollment every 4 months, with the expectation that the independent monitor will provide input on enrollment within 30 days. UPs and AEs will be reported to the independent monitor within 24 hours with the expectation that the independent monitor will provide input on UPs and/or AEs within 5 days.

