REDCap is housed on a secure, climate-controlled server. UNC has in place an IT Security Plan as required by NIH contracts and grants. As part of the plan, the principle of least access privilege for study files is implemented. Included in the plan are a risk assessment, a system continuity plan, and a disaster recovery plan. Support for REDCap services is provided by the NC TraCS Institute, the Clinical and Translational Science Award center at UNC-CH.

Data confidentiality and security measures will be applied at all levels of TEMPO data acquisition, transfer and storage. REDCap meets exacting data management standards of confidentiality, as well as HIPAA requirements. Beyond the password-controlled access to REDCap, data are encrypted by the system and can only be decrypted for display on-screen by authorized study personnel. Personal identifiers are collected on separate forms as an additional safeguard against linking of identifiers and medical information.

Enrollment and other data management reports will be available from the REDCap database. Monthly reports on study enrollment, intervention, unexpected events, and adverse events will be provided to the principal investigator and

quarterly reports will be provided to the independent monitor. Annual progress reports will be submitted to NIH and to the University of North Carolina IRB.

Study records will be maintained for at least three years from the date that the grant federal financial report (FFR) is submitted to the NIH.

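### Home-phase adverse events and readmissions are in scope, but no post-discharge contact is described as routinely asking about them, most clearly between the first follow-up and the 12-month visit

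*Combined protocol and SAP*

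**What the plan says.** **Scope.** Section 8 defines an AE as "any untoward medical occurrence in a subject during participation in the clinical study", whether or not it is related to the study. One criterion for an SAE is that the event "Results in inpatient hospitalization or prolongation of existing hospitalization". The synopsis says that each dyad's "participation will last approximately 15 months", and section 4.3 continues the home-program reminders until the 12-month visit.

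**Contacts after discharge (section 4.3).** There is one telephone call within two weeks. Bi-weekly emails run up to the first follow-up and again from there to 12 months. In both runs the plan states: "These emails will include a link for parents to report frequency of PT intervention and massage at home". The first follow-up includes a massage review that also covers safety concerns and changes in the infant. The 12-month visit has the Bayley assessment, the parent questionnaires, the PAQ and an interview.

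**Other sources (section 5).** The infant items under "Variables that will be abstracted from medical charts" are name, date of birth, gestational age, birth weight, race/ethnicity and cortisol. The interview examples include "how often they did massage and for how long, did they find the massage easy to do on an ongoing basis".

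**Review and reporting.** Section 8 states that "UPs and AEs will be reported to the independent monitor within 24 hours". Section 9 adds that "Monthly reports on study enrollment, intervention, unexpected events, and adverse events will be provided to the principal investigator". The section 6.4 table schedules AE review by the PI and the independent monitor, and review of the status of enrolled subjects monthly by the PI and quarterly by the monitor.

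**The concern.** The AE definition covers the whole of participation, but the data collection described for the home phase measures how often parents deliver the program, not what happens to the infant. In hospital, sessions are attended by staff and section 5.1 sets out active monitoring. At home the parent works alone, and the plan does not say how an event would come to be recorded.

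Three safety judgements draw on these records: the Annual Report's comparison of AE rates with pre-study assumptions (section 9), the rule for stopping the study on AEs (section 8), and the rule for withdrawing an infant after a related severe AE or SAE (section 8, Halting Rules). Section 8 itself says that massage has been studied less in infants below 28 weeks. A low home AE rate could mean that the program is safe or that nobody asked, and the planned data could not tell these apart.

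**Working it through.** The plan gives no figure for home AE ascertainment, so there is none to reproduce. The check is a comparison of the text, followed by simple arithmetic.

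**1. Does any described contact ask about events?**
- Two-week call: discharge education, home program, massage technique, parent's questions. No event question stated.
- Bi-weekly link: frequency of interventions and massage. No event question stated.
- First follow-up: safety concerns are addressed within the massage review. No AE form, recall period or readmission question stated.
- 12-month visit: Bayley, questionnaires, PAQ, interview. No event question stated.
- Table 1: no AE row.
- Chart abstraction: no AE, diagnosis or readmission item.
- PI's weekly completeness check (section 9): vital signs, cortisol, bedside and home intervention reports, questionnaires. No AE form.

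**2. Do the review provisions fill the gap?** The reviews in section 6.4 and the database reports in section 9 work on what has been recorded. Several section 8 reporting clocks start when the investigator becomes aware of an event. The part of section 8 whose title refers to event assessment gives only reporting times to the monitor. None of these says how a home event is found.

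**3. How long is the weakest stretch?** Bi-weekly is read as every two weeks.
- Upper end: the synopsis places the clinic visits at 2 and 12 months corrected age. 12 − 2 = 10 months; 10/15 = 67% of participation; 30 × 10 = 300 dyad-months.
- Lower end: section 4.3 numbers the emails before the first follow-up as approximately visits 2 to 12, which is 11 emails. 11 × 2 = 22 weeks; 22 ÷ (52/12) = 5.1 months after discharge. If discharge is near term (an assumption), the first follow-up falls at about 5 months corrected. 12 − 5 = 7 months; 7/15 = 47%; 30 × 7 = 210 dyad-months.
- If only the 70% retention goal is met and lost dyads contribute nothing to this stretch (an assumption), 21 dyads give 21 × 7 = 147 to 21 × 10 = 210 dyad-months.

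**4. What would partial ascertainment do?** The documents give neither a home event rate nor a capture rate, so this is illustration only. If a fraction c of affected infants is captured, the expected observed proportion is c times the true one. With no affected infant seen among 30, the exact one-sided 95% upper bound is 1 − 0.05^(1/30) = 9.5% at full capture. At c = 0.50 it is 9.5%/0.50 = 19%, and at c = 0.25 it is 38%. If 10% of infants truly had a home SAE and half were captured, the chance of seeing none would be (1 − 0.10 × 0.50)^30 = 21%. With 30% affected it would be (1 − 0.30 × 0.50)^30 = 0.8%.

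**5. What load would a broad question on the link create?** Links per dyad: 7 × (52/12) ÷ 2 = 15.2, or 10 × (52/12) ÷ 2 = 21.7. For 30 dyads that is 455 to 650 links. Taking the 50% reporting goal as the share of links answered (an assumption), 228 to 325 are answered. If 20% to 40% of answers to an open health question were yes (an assumption), this stretch would generate about 46 (228 × 0.20) to 130 (325 × 0.40) calls and AE forms.

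**The case against.** A reader might infer that home events can reach the study only if a parent volunteers them. The documents do not support that. The first follow-up session is led by staff and takes up safety concerns and infant changes. Both follow-up visits are with the multidisciplinary neonatology team. The status of enrolled subjects is reviewed monthly, although the plan does not say how status is obtained. Parents hold the therapist's email and pager details. Section 6.1 refers to a structured interview guide and section 9 to case report forms; neither is in the documents, nor is the form behind the link. Any of them might contain an event question. The gap is therefore in what the plan describes, and absence of all ascertainment cannot be shown.

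It would also be wrong to quote two thirds of participation as the size. That rests on one reading of the first follow-up date, and the plan's own email numbering points to something nearer 7 months.

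The consequence has limits too. The per-infant halting rule needs an event related to the intervention, so an unrelated readmission would not trigger it. Section 8 treats unrelated SAEs as less urgent. In a single-group study without hypothesis tests, a readmission count can say little about causation.

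These points narrow the concern but do not remove it. None identifies a routine enquiry for the stretch after the first follow-up. The protocol also sets itself the task of judging AE rates, which needs a known method of collection even without a control group.

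**Conclusion.** The concern holds as a gap in systematic ascertainment, and the protocol should be changed. Events and admissions at home are in scope, no described post-discharge contact routinely asks about them, and the review schedule governs only events already known. Followed as written, the plan would probably under-count home events in the Annual Report rates and in the stopping and halting judgements. The documents do not allow the size of the undercount to be estimated.

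The clearest gap lasts about 7 to 10 of about 15 months (47% to 67%). The range depends on when the first follow-up falls; its lower end also assumes emails every two weeks and discharge near term. If the unseen link form, interview guide or case report forms already contain an event question, what remains is to say so in the protocol.

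**What to change.** (a) Add one short item to the existing bi-weekly link. It asks whether, since the last answered report, the infant has had a skin reaction, a breathing or color change or distress with massage or physical therapy interventions, an emergency visit, or a hospital admission. A yes leads to a study-team call and an AE form.

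(b) Ask the same item, plus a general health-event question, at the two-week call, the first follow-up and the 12-month visit. Add an AE row to Table 1.

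(c) Add readmissions and emergency visits at the study hospital to the chart-abstraction list. This is a backstop only, because admissions elsewhere will not appear there.

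(d) Report home AEs together with the share of home time covered by an answered item, so that a low count can be read against how much time was actually asked about.

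The cost is a protocol amendment, one item on an existing link and at three existing contacts, and a small addition to chart abstraction. No new visits are needed. Parents report slightly more, on a link whose response is itself a feasibility measure. Staff take on a number of follow-up calls and AE forms, with the monitor notified within 24 hours under the current section 8. Limiting the link item to the listed events, and keeping the open health question for the three staff-led contacts, keeps that load modest.

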## 1 BACKGROUND AND RATIONALE

## **1.1 Introduction**

The Therapist Education and Massage for Parent-Infant Outcomes program (TEMPO) is a structured, therapist-led PT program developed by the applicant based on her clinical experience. TEMPO trains and supports parents to deliver PTIs such as massage and developmental play during hospitalization and in the home setting. The goal of this project is to assess the feasibility and acceptability of TEMPO for parents of EP infants born in the Neonatal Critical Care Center (NCCC) at UNC Children's Hospital.

There are several innovative aspects to this research. First, the TEMPO program enhances standard care by structuring the nature and frequency of therapist-parent interactions to increase the parent's comfort level with administering massage and developmental activities with their EP infant. In standard care, parent education during hospitalization is provided spontaneously if the parent is available, does not include infant massage, does not use supplementary written materials or resources, and does not include check-ins with a therapist post-discharge. Second, this project will recruit parents of infants <28 weeks gestation, a population that has not been studied in previous research on massage. Third, the TEMPO program emphasizes the critical role therapists can have not only in educating and supporting parents of EP infants, but in developing and rigorously testing complementary/integrative health approaches in unique patient populations. Finally, once TEMPO is further developed it can be adapted to evaluate other complementary/integrative health approaches for the EP population and other high-risk infant populations (e.g., neonatal drug withdrawal, infants with hypoxic ischemic encephalopathy).

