#### *During infant hospitalization*

- **Visit 1: Early Parent Education Session:** Initiated within 3 weeks of infant birth. The PT will educate the parent about the importance of infant positioning, the impact of prematurity on the motor and sensory systems, and how to read and respond to infant behavioral-motor cues using a written pamphlet with pictures to supplement the verbal education lasting about 30 minutes.
  - At this visit, the therapist will have the parent fill out the following questionnaires for baseline measurement: AIM, FIM, PROMIS, CESD, EPDS, PSOC
  - The therapist will also ask the parent to complete a contact information form and a demographic form.
- **Visits 2-8: Weekly Parent Education Sessions <34 weeks:** Following the initial parent education session, the PT will hold weekly parent education sessions, ideally at the time of therapy. When the infant is this young (<34 weeks gestation), PT intervention and education will focus on infant behavioral-motor cues, reading/response to infant cues, positioning strategies/concerns, and developmentally appropriate stimulation of the infant. If the parent is not available for all therapy sessions, then the parent will receive a weekly update about their infant's progress face-to-face and/or via video chat.
  - Parents will be asked to record the frequency of physical therapy interventions on a bedside card.
- **Visits 9-10: Infant Massage Parent Education Sessions:** Parent-administered infant massage will be incorporated into the therapy plan of care as soon as the infant's medical provider determines that the infant is physiologically stable and can tolerate massage. This time is generally once the infant is approximately 34 weeks gestational age, approximately 1500 grams, and is demonstrating temperature stability out of the isolette for short periods. At a minimum, the therapist will teach massage for the back or lower extremities over 2 parent education sessions. The therapist will demonstrate massage strokes on a doll using verbal cues to guide the parent while the parent administers massage on the infant. An instructional massage pamphlet will be provided. Once the therapist has determined parent safety with massage administration, parents will be encouraged to practice infant massage when they visit the baby and to note when they do this by marking a card at the bedside.

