## 6 STATISTICAL CONSIDERATIONS

### 6.1 Primary Objectives

No hypothesis tests will be performed in this study. The primary goal of this project is to test feasibility and acceptability of the TEMPO program and study protocol (Aim 1). As such, the analysis plan will not focus on inferential statistics but on measures of feasibility identified in the NCCIH's *Framework for Developing and Testing Mind and Body Interventions* (<https://nccih.nih.gov/grants/mindbody/framework>):

- Recruitment: Percentage of eligible infant-parent dyads who enroll in the study (Goal  $\geq 55\%$ )
- Willingness to be randomized: Percentage of enrolled parents who, in interviews, report they would agree to be randomized (Goal  $\geq 70\%$ )
- TEMPO delivered per protocol: Percentage of enrolled parents who complete all TEMPO components per protocol (Goal  $\geq 70\%$ ) and weekly and bi-weekly reporting of physical therapy interventions (goal  $\geq 50\%$ ).
- Retention: Percentage of enrolled parents who are retained in the study at 12 months (Goal  $\geq 70\%$ ), reasons for attrition for those who do not complete the protocol
- Complete data collection: Percentage of enrolled parents who complete data collection, including interviews (Goal  $\geq 70\%$ )
- Adherence: Percentage of enrolled parents who complete at least 2-3x/week during hospitalization and 2-3x/week in-home PTIs as noted on the parent log or survey (Goal  $\geq 70\%$ )
- Acceptability and Feasibility of TEMPO: Percentage of parents who rate acceptability and feasibility as 4/5 or 5/5 using the Acceptability of Intervention Measure and the Feasibility of Intervention Measure (Goal  $\geq 70\%$ )
- Acceptability of the Protocol: A structured interview guide will be followed by the PI or research coordinator. Interviews will be audio recorded and transcribed by a confidential online service. All audio files will be stored and transmitted using TLS 1.2 encryption for a high level of security. Interviews will be coded by the PI for content and qualitative analysis to derive themes. (Aim 1 and 2)

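### The therapist gives parents the AIM and FIM, and the PI may run the acceptability interview, leaving a primary goal open to courtesy bias that the study coordinator could reduce

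*Combined protocol and SAP*

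**What the plan says.** **Who gives out the ratings.** In section 4.2, at the early education session, "the therapist will have the parent fill out the following questionnaires for baseline measurement: AIM, FIM, PROMIS, CESD, EPDS, PSOC". The discharge visit (4.2), the first follow-up visit and the 12-month visit (both 4.3) use parallel wording: "the therapist will have the parent fill out the following questionnaires for ongoing measurement", and the list that follows again includes the AIM and FIM. The first three of these visits also deliver TEMPO content: early education, discharge education and the massage review. At 12 months the PT administers the Bayley assessment.

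**Who interviews.** At the first follow-up and 12-month visits, "the PI or study coordinator will interview the parent about acceptability of the TEMPO program". Section 5 adds the randomization question to that interview: "We will also ask about willingness to have participated in this study if it were a randomized trial". Under section 6.1 the PI also codes the interviews.

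**What depends on it.** Section 6.1, under Primary Objectives, sets a goal of at least 70% for this measure: "Percentage of parents who rate acceptability and feasibility as 4/5 or 5/5". It sets the same goal for willingness to be randomized, which is taken only from the interviews.

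**Who built the program.** Section 1.1 describes TEMPO as a "structured, therapist-led PT program developed by the applicant based on her clinical experience".

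**Safeguards present.** Surveys are completed on an iPad (sections 4.1 and 9). Interviews follow a structured guide and are recorded and transcribed by an outside service (6.1). The example questions include what parents disliked (5).

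**The concern.** Parents are asked to rate a therapist-led program by a therapist, usually in the session where that program is being delivered. Section 1.3 lists a strong relationship with the therapy team as a possible benefit of TEMPO, and the team stays in touch by phone and email after discharge. A parent with reservations has some reason to score generously.

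The iPad does not settle this. Section 9 gives accurate interpretation of data as its purpose, and no section says that the therapist steps away or cannot see the answers. The structured guide fixes what is asked in the interview, not who asks it.

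At stake is whether the AIM and FIM result can be taken at face value when the next trial is planned. The study has one group, so no comparison would expose inflated ratings. The confidence intervals promised in section 6.3 cover sampling error only.

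**Working it through.** **1. The plan's own sizing figure.** Section 3.2 gives about 57 eligible infants and a 55% enrollment goal: 57 × 0.55 = 31.35, consistent with the proposed 30 dyads. That figure is not in dispute.

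**2. The count that meets the goal.** 0.70 × 30 = 21 parents. One courtesy answer turns 20/30 (66.7%) into 21/30, and three turn 18/30 (60%) into 21/30. The exact 95% confidence interval at 21/30 is 50.6% to 85.3%, and it would look the same whether or not the answers were inflated.

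**3. Illustration of size.** The documents give neither the true favorable rate nor the amount of courtesy inflation, so both are assumed. Let *p* be the true proportion who would privately score 4 or 5, and *s* the share of the remaining parents who give a 4 or 5 because of who is asking. The expected observed rate is *p* + *s*(1 − *p*). For *p* = 0.60 and *s* = 0.10 this is 0.60 + 0.10 × 0.40 = 0.64. The chance of at least 21 of 30 is then an exact binomial tail, assuming all 30 respond.

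| True rate | Observed rate at *s* = 0, 0.10, 0.20 | Chance of ≥21/30 at *s* = 0, 0.10, 0.20 |
|---|---|---|
| 50% | 50%, 55%, 60% | 0.021, 0.069, 0.176 |
| 60% | 60%, 64%, 68% | 0.176, 0.316, 0.494 |
| 70% | 70%, 73%, 76% | 0.589, 0.725, 0.838 |
| 80% | 80%, 82%, 84% | 0.939, 0.968, 0.985 |

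**4. Does the number of respondents matter?** If only 21 parents respond (70% of 30, the retention goal), the goal is 15/21, since 0.70 × 21 = 14.7. At a true 60% the chances are 0.20, 0.32 and 0.47. At the ceiling of 40 dyads the goal is 28/40 and the chances are 0.13, 0.27 and 0.47. A larger sample does not cure the problem.

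**5. Is the PI the developer?** Section 1.1 credits *the applicant*. Sections 3.1 and 10 mention the PI alongside a grant mentor. That the PI is the applicant is the natural reading, but no section states it.

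**6. Who else could do it?** Section 4.3 already allows the study coordinator to interview, and section 9 already has the coordinator collecting and managing data. The other channel in the plan, the survey link in the bi-weekly emails, is no substitute. The PT sends those emails (4.3), and section 9 has all surveys completed on an iPad.

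**The case against.** The other side has real points, and several limit what can be claimed.

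- **Safeguards exist.** Parents complete the forms themselves, interviews are structured and recorded, and parents are asked what they disliked. These help, but none keeps an individual rating from the therapist.
- **The instruments rate the intervention, not the therapist.** True, but the intervention is therapist-led, so the two are hard for a parent to separate.
- **A reader might infer that the therapist asking has treated the family for months.** The documents do not establish this. At baseline delivery has only begun, and at follow-up the text refers to *the PT* or *a PT*, who may not be the inpatient therapist.
- **A reader might infer that willingness to be randomized is also biased upward.** The documents do not support a direction. A parent wishing to please could say yes to help the research, or no to show how much the program is valued. Who asks may influence the answer, but which way is uncertain.
- **A reader might treat 21/30 as a pass mark.** Section 6.1 states that no hypothesis tests will be performed, and no go/no-go rule is attached to the 70% goals. The probabilities above only show how sensitive the observed result is.
- **A reader might expect the coordinator to eliminate the problem.** The coordinator also introduces the study (10), explains it at consent (11) and may collect the cortisol swabs (4.2), so is not neutral.

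**Conclusion.** The concern holds for the AIM and FIM. As written, the plan leaves the acceptability and feasibility ratings open to courtesy bias toward the 70% goal, through an arrangement that staff already named in the plan could improve. For willingness to be randomized, the conclusion is only that the interviewer may affect the answer.

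The size is unknown. Under the assumed 10% to 20% shift with 30 respondents, the effect on the chance of observing at least 21/30 is greatest at true rates of 60% and 70% (0.18 to 0.32–0.49, and 0.59 to 0.72–0.84). It is smaller at 50% (0.02 to 0.07–0.18) and slight at 80% (0.94 to 0.97–0.98). If TEMPO is in fact widely liked, the result will change little. The change is worth making because it is cheap and protects a measure listed under Primary Objectives.

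**What to change.** 1. **Sections 4.2 and 4.3.** At all four time points, have the study coordinator rather than the therapist hand over the iPad for the AIM and FIM. The therapist and PI should not be present, and parents should be told that neither will see individual ratings. Section 6.1 does not say which time point counts toward the goal, so all four need the change.
2. **Sections 4.3, 5 and 6.1.** Make the coordinator the only acceptability interviewer. The PI can still code transcripts once they are de-identified.
3. **Section 9.** The PI reviews questionnaires weekly for completeness. For the AIM and FIM, limit that review to completion status; otherwise the assurance in item 1 would not be true.
4. **Do not move the AIM and FIM to the existing email link.** The therapist would remain the one asking. The plan also sets a lower goal for the weekly and bi-weekly reporting that uses the bedside card and that link (at least 50%) than for complete data and interviews (at least 70%), so non-response could become the larger problem.

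The cost is protocol wording, some coordinator time and less flexible visit scheduling. No new staff and no change in sample size are needed.
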